#### **Project Description:**

This is a randomized, prospective trial with the primary aim of evaluating the effectiveness of intraoperative topical steroids in decreasing the severity of swallowing difficulty following anterior cervical fusion surgery.

Principal Investigator:

[name]

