#### Outcomes:

To determine if topical steroids placed intraoperatively in the wound of an anterior cervical discectomy and fusion surgery reduce the incidence of postoperative swallowing difficulty using the SWAL-QOL outcome measure. SWAL-QOL will be administered pre-operatively, on post-operative day one, post-operative day two, post-operative 4-6 weeks, post-operative 3 months, post-operative 6 months, and post-operative 12 months. Differences in SWAL-QOL scores will be stratified based on levels fused (2-, 3-, and 4-levels).

The Bazaz Dysphagia Score and the Eating assessment Tool 10 (EAT-10) will be administered at the same time points to provide additional data about swallowing difficulty

Additionally, questionnaires that assess how neck and arm related pain affects the patient's quality of life will be administered pre-operatively (NDI & VAS), post-operatively day 1 and 2 (VAS), week 4-6 (NDI & VAS), month 3 (NDI & VAS), month 6 (NDI & VAS), and at month 12 (NDI & VAS).

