#### Interventions and Observations:

We plan to observe the effect on SWAL-QOL scores in patients following ACDF in groups that either receive or do not receive intraoperative topical steroid. All individuals undergoing 2-4 level ACDF that meet the inclusion criteria will be randomized to either: 1) treatment arm or 2) control arm. Both arms will undergo their planned surgeries and will receive the exact same procedure and standard of care as if they were not enrolled in a study. The only difference is that the treatment arm will receive 40 mg of Depo-Medrol delivered with one SURGIFLO Hemostatic Matrix Kit (Ethicon, Somerville, NJ, USA) injectable delivery vehicle prior to closure in the prevertebral soft tissues. The control group will receive only SURGIFLO Hemostatic Matrix Kit prior to closure. The surgeon will inject the material directly in the pre-vertebral soft tissue.

Both groups will have the same standard evaluations both pre-operatively and post operatively. The SWAL-QOL questionnaire will be utilized as the primary instrument to measure outcome. Other questionnaires, the EAT-10 and Bazaz Dysphagia Score, which grades will be used to assess dysphagia and swallowing difficulty. Additionally, the Neck Disability Index and the Visual Analog Scale for neck and arm pain will be administered to assess how neck related pain impacts the patients' quality of life. The EAT-10, Bazaz, and Visual Analog scale will be utilized to assess secondary outcomes. These questionnaire will be given to the patients to complete pre-operatively, on post-operative day one, post-operative day two, at post-operative week 4-6, post-operative month 3, post-operative month 6, and post-operative month 12. The Neck Disability Index will be completed pre-operatively, at post-operative week 4-6, post-operative month 12.

All test or images are standard of care. Administration of the EAT-10, SWAL-QOL survey, Neck Disability Index, VAS (Neck and Arm Pain), and Bazaz Dysphagia Score are not standard of care. Funds are not required for administration of these questionnaires.

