# **Statistical Plan:**

Steroid and Control arms were compared in terms of demographics and surgical information using a student's independent t-test and chi square/fisher exact test for normally distributed data, and a Mann-Whitney U test otherwise. In terms of PROs, a Mann-Whitney U test was performed to compare the group medians for dysphagia scores at Baseline, Post-op Day 1, Post-op Day 2, post-operative week 4-6, post-operative month 3, post-operative month 6, and post-operative month 12. In addition, a pre-post op comparison was conducted by calculating the change in PRO from baseline to each post-operative time point for each patient. Statistical significance was determined for all results with p<0.05.

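### SWAL-QOL is primary at six post-operative visits, each tested at p<0.05 against one null, with no primary visit, primary form of the score or multiplicity rule

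*Combined protocol and SAP*

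**What the plan says.** **Primary instrument.** Under Interventions and Observations: "The SWAL-QOL questionnaire will be utilized as the primary instrument to measure outcome". No visit is attached. The same section makes EAT-10, Bazaz and VAS secondary.

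**Visits.** Under Outcomes: "SWAL-QOL will be administered pre-operatively, on post-operative day one, post-operative day two, post-operative 4-6 weeks, post-operative 3 months", followed by 6 and 12 months. That is one baseline and six post-operative assessments.

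**Null.** The Hypothesis section gives one null, of no difference in swallowing difficulty between the arms.

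**Analysis.** Under Statistical Plan: "a Mann-Whitney U test was performed to compare the group medians for dysphagia scores at Baseline, Post-op Day 1, Post-op Day 2", and so on through month 12. It adds that "a pre-post op comparison was conducted by calculating the change in PRO from baseline to each post-operative time point for each patient". It ends: "Statistical significance was determined for all results with p<0.05".

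**Form of the outcome.** The Project Description aims at "decreasing the severity of swallowing difficulty following anterior cervical fusion surgery". Outcomes asks instead whether the steroid will "reduce the incidence of postoperative swallowing difficulty using the SWAL-QOL outcome measure", with no SWAL-QOL cut-off that would define a case. Outcomes also says: "Differences in SWAL-QOL scores will be stratified based on levels fused (2-, 3-, and 4-levels". Whether those stratified results are primary is not said.

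**The concern.** Naming an instrument does not name an endpoint. One null is exposed to at least six between-arm tests, each at the full 0.05, and no rule turns six p-values into one decision. If visits disagree, or if scores, change and incidence disagree, the plan cannot say whether the null is rejected. A single significant visit could be reported as evidence that the steroid reduces swallowing difficulty, at an error rate well above the nominal one. The Background section looks ahead to adoption of the steroid if it is shown to be safe and effective, so the reliability of that one claim is what is at stake.

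**Working it through.** **Inputs from the documents.** Six post-operative SWAL-QOL visits (Outcomes); a separate Mann-Whitney test at each, all judged at 0.05 (Statistical Plan); one null (Hypothesis); 128 patients (Target Enrollment). The baseline comparison is left out because it does not test the treatment.

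**Assumptions.**
- Testing is two-sided. Sidedness is not stated, but the null is one of no difference.
- The arms are equal, 128/2 = 64 each.
- There is no dropout.
- The between-visit correlation r is the same for every pair of visits, from 0.3 to 0.7, with 0.9 and independence as limits.
- One significant visit rejects the null.

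**The plan's own figure.** The plan states no overall error rate or power. The 128 cannot be reproduced, because no effect size, SD, power or dropout is given. As an assumption only, 0.50 SD with 80% power at 0.05 needs 63 per arm, or 126 in total.

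**Step 1: chance of at least one p<0.05 with no true effect.**
- Independent visits: 1 − 0.95^6 = 26.5%.
- Correlated visits: 1 − ∫ φ(u) [Φ((c − √r·u)/√(1−r)) − Φ((−c − √r·u)/√(1−r))]^6 du, with c = 1.960.
- In favour of the steroid only: 1 − ∫ φ(u) [Φ((c − √r·u)/√(1−r))]^6 du, with the same c.

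| r | Any visit, two-sided | Any visit favouring steroid | Holm, two-sided | Holm, favouring steroid |
|---|---|---|---|---|
| 0.3 | 24.1% | 12.2% | 4.6% | 2.3% |
| 0.5 | 20.7% | 10.4% | 4.1% | 2.1% |
| 0.7 | 16.4% | 8.2% | 3.3% | 1.7% |
| 0.9 | 10.8% | 5.4% | 2.1% | 1.1% |

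Holm's first step compares the smallest p with 0.05/6 = 0.0083, so its columns use c = 2.638 in the same formulas. The two-sided rate for unadjusted testing returns to 5% only at r = 1.

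**Step 2: checks.** Simulated Mann-Whitney tests with 64 per arm gave 24.6%, 21.0% and 16.8% at r = 0.3, 0.5 and 0.7. With correlation that decays between visits (first-order autoregressive) the figures were 25.4%, 23.5% and 19.8%. The range does not hinge on the normal approximation. The decaying pattern moves it upward.

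**Step 3: what Holm costs in power (normal approximation).**
- Detectable difference at 80% power: (1.960 + 0.842)·√(2/64) = 0.50 SD at 0.05, and (2.638 + 0.842)·√(2/64) = 0.62 SD at 0.05/6.
- A 0.50 SD effect at one visit has expected z = 0.50/√(2/64) = 2.828. Power is Φ(2.828 − 1.960) = 81% at 0.05 and Φ(2.828 − 2.638) = 58% at 0.05/6.
- A 0.50 SD effect at all six visits is found by Holm at one or more visits in 95.2%, 90.3% and 83.5% of trials at r = 0.3, 0.5 and 0.7.

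**The case against.** **The any-one-visit rule is not in the plan.** This is the strongest objection, and it stands as a limit on the numbers. A reader might infer that the plan adopts this rule, or that 16-24% is the trial's actual error rate. The documents support neither. What they do show is that the rule is not excluded while every result is judged at 0.05. The missing decision rule is a fact at any correlation.

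**The two-sided figure overstates the feared error.** A false claim of benefit is the harm in view, and for that the figure is 8-12% against 2.5%. Both figures are therefore given. The directional one is still about three to five times nominal.

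**A lone significant visit might be read as probably due to chance.** That inference does not hold. With no effect, at r = 0.9 only about 36-37% of trials with any significant visit have exactly one. If a 0.50 SD effect truly exists at a single visit, 88-91% of trials with any significant visit have exactly one. The pattern does not separate chance from a real one-visit effect.

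**Change scores might seem to double the number of tests.** The Statistical Plan says that change is calculated for each patient. It does not say that change is tested between arms, and the comparison could be within arm. No figure for such tests is used here.

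**Holm is a preference.** This is fair. One global test across visits would also fit a single null. Holm is suggested because it keeps the test already named and shows which visits carry the effect. Treating scores as primary over incidence is likewise a choice. The severity aim and the named test support it, but the sponsor has to confirm it.

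**Conclusion.** The point holds and should be fixed before the result is interpreted. The primary analysis is undefined as to visit, form of the score and decision rule, and the only significance rule in the plan does not hold 5% for the single null if any one visit counts. On that reading the false-positive chance is about 16-24% two-sided and 8-12% in favour of the steroid, for an assumed correlation of 0.7 to 0.3 (two-sided about 11% at 0.9, 26.5% if independent). These figures are conditional on the any-visit reading, two-sided testing and the assumed correlation. The gap in the plan depends on none of them.

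**What to change.** Replace the closing sentence of the Statistical Plan with:

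> *Demographic and surgical comparisons use p<0.05. The primary hypothesis is tested by the between-arm Mann-Whitney comparison of SWAL-QOL scores at the six post-operative visits, with Holm adjustment to a two-sided familywise 0.05. The null is rejected if at least one Holm-adjusted p is below 0.05. Claims are limited to the visits and directions that are significant after adjustment; significant visits in opposite directions are reported as such and not as overall benefit. EAT-10, Bazaz and VAS are secondary. NDI, change from baseline, any incidence result and results by levels fused are exploratory. None of these can establish efficacy on its own.*

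The sponsor should also reconcile severity (Project Description) with incidence (Outcomes).

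**Alternative, only if outcome data are unseen.** Name one visit, one form of the score and one test as primary at two-sided 0.05, and test the other five visits by Holm only if that test is significant. A non-significant primary visit then blocks confirmatory claims at the rest.

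**If outcomes have been seen.** The past tense of the Statistical Plan may suggest this but does not establish it. In that case do not pick a primary visit, and label the Holm adjustment post hoc. It then corrects the reported error rate but does not restore confirmatory status.

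**Cost.** Wording only, with no new data. The price is power for an isolated effect: about 81% down to about 58% for 0.50 SD at one visit, or a detectable difference of 0.62 rather than 0.50 SD. Both assume 64 per arm and no dropout. With an assumed 20% loss (51 per arm) the same formula gives 0.69 and 0.55 SD. An effect of 0.50 SD at all visits would still be found at one or more visits in about 83.5-95% of trials (64 per arm, correlation 0.7 to 0.3).

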## Hypothesis:

The null hypothesis is that there will be no difference in swallowing difficulty between patients who do and patients who do not receive intraoperative topical steroids in the wound at the end of the surgical case.

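### The p<0.05 rule covers every result and does not carry the SWAL-QOL ranking into testing, so EAT-10 or Bazaz at any post-operative visit can be declared significant without SWAL-QOL support

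*Combined protocol and SAP*

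**What the plan says.** **Ranking of instruments.** Interventions and Observations states: "The SWAL-QOL questionnaire will be utilized as the primary instrument to measure outcome". The same section adds: "The EAT-10, Bazaz, and Visual Analog scale will be utilized to assess secondary outcomes". The Outcomes section ties the objective to SWAL-QOL and gives EAT-10 and Bazaz a supporting role: they "will be administered at the same time points to provide additional data about swallowing difficulty".

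**Null hypothesis.** The Hypothesis section says "there will be no difference in swallowing difficulty between patients who do and patients who do not receive intraoperative topical steroids". It names neither a scale nor a visit. The primary aim in the Project Description also names no instrument.

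**Tests.** In the Statistical Plan, "a Mann-Whitney U test was performed to compare the group medians for dysphagia scores at Baseline, Post-op Day 1, Post-op Day 2", and then at "post-operative week 4-6, post-operative month 3, post-operative month 6, and post-operative month 12". That is baseline plus six post-operative visits. The plan speaks of dysphagia scores in general and does not separate the three swallowing scales. It adds a pre-post comparison made by "calculating the change in PRO from baseline to each post-operative time point for each patient".

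**Decision rule.** The section closes with "Statistical significance was determined for all results with p<0.05". It gives no primary visit, testing order, multiplicity adjustment or exploratory label.

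**The concern.** The ranking appears in the sections that describe the instruments but not in the section that decides what is significant. EAT-10 and Bazaz measure the same construct as the primary instrument, and the null is worded in terms of that construct. A significant EAT-10 or Bazaz difference at any one visit can therefore be presented as rejecting the null as written, even when SWAL-QOL shows nothing.

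At stake is which claims the trial may make. A chance finding on a scale of the same construct reads as confirmation of the main claim. Naming a primary SWAL-QOL visit would not by itself cure this, because the EAT-10 and Bazaz tests would still each be declared at 0.05.

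**Working it through.** **Inputs from the documents**
- Threshold: 0.05 for each result (Statistical Plan). This is a chosen threshold, so there is no derived figure to reproduce.
- Post-operative visits: 6 (day 1, day 2, week 4-6, months 3, 6 and 12).
- Secondary swallowing scales: 2 (EAT-10, Bazaz), given at the same visits as SWAL-QOL.
- Secondary between-arm tests: 2 x 6 = 12. Baseline is not counted. Change scores are also left out, because the plan does not say clearly that they are compared between arms.

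**Assumptions.** Tests are two-sided (the plan does not say), test statistics are approximately normal, and steroid has no effect on any scale. Correlations between visits and between scales are assumed, because the documents give none.

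**Step 1: at least one significant result among the 12.** If the tests were independent, 1 - 0.95^12 = 0.460. With a common correlation r and c = 1.96, the rate is

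1 - E{ [Φ((c - √r·X)/√(1-r)) - Φ((-c - √r·X)/√(1-r))]^12 }, with X standard normal.

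| r | Rate |
|---|---|
| 0.3 | 0.397 |
| 0.5 | 0.319 |
| 0.7 | 0.232 |
| 0.9 | 0.135 |

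This counts results in either direction, whether or not SWAL-QOL agrees.

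**Step 2: a secondary result favouring steroid without a SWAL-QOL benefit.** I simulated 18 correlated statistics (3 scales x 6 visits). The correlation between two tests was the between-visit value times the between-scale value, with 1 used for the same visit or the same scale. The event is EAT-10 or Bazaz significant in favour of steroid at some visit, with no significant SWAL-QOL benefit.

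| Between visits / between scales | SWAL-QOL judged at one fixed visit | SWAL-QOL judged at any visit |
|---|---|---|
| 0.3 / 0.3 | 20.9% | 17.6% |
| 0.5 / 0.5 | 16.4% | 12.9% |
| 0.5 / 0.7 | 14.6% | 10.1% |
| 0.7 / 0.8 | 10.3% | 6.6% |

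**Step 3: one visit only.** With all three swallowing scales tested at a single visit, the Step 1 formula with exponent 3 gives 0.125 at r = 0.5. SWAL-QOL's own permitted error is 0.05, so the secondary-only part is 0.125 - 0.05 = 0.075. About half of that, 3.8%, favours steroid. Most of the Step 2 figure therefore comes from the six visits, not from having three scales.

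**Step 4: what a gate must look like.** SWAL-QOL tested at six visits is significant at one or more of them in 24%, 21% and 16% of trials at between-visit correlations of 0.3, 0.5 and 0.7. A gate that opens on any SWAL-QOL visit therefore does not hold 5%. A gate on SWAL-QOL at one named visit limits false secondary claims to at most 5% under no effect, because the gate itself opens that rarely.

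**The case against.** The strongest reply is that the documents do rank the instruments. The Outcomes section attaches the objective to SWAL-QOL and describes EAT-10 and Bazaz as additional data, and Interventions and Observations labels them secondary. A careful reader would discount a finding on a secondary scale alone. Unadjusted secondary tests are also acceptable when no confirmatory claim rests on them, and no sentence says one will.

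Much of this stands. A reader might infer that the Statistical Plan abolishes the ranking, but it is only silent on it. A reader might also set the 23% to 40% against the plan's 0.05 as a multiple of a promised error rate. The 0.05 is a per-result threshold, and no family-wise rate is claimed for secondary outcomes. Nor does that range measure unsupported benefit claims, since it includes results against steroid and results that SWAL-QOL confirms. Finally, pain VAS and NDI should not be added to the count: the between-arm Mann-Whitney test is specified for dysphagia scores only, and a pain scale cannot reject a null about swallowing.

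What does not stand is the idea that a label is enough. The only rule on significance covers all results, none is declared exploratory, and the null names no scale.

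It is also fair to say that the missing primary SWAL-QOL visit is the more basic gap, and that any hierarchy depends on closing it first. The fixed-visit column shows that the secondary problem remains once a visit is named.

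**Conclusion.** The point holds in a limited form. The plan ranks the scales but does not carry the ranking into its decision rule, and the null is looser than the objective. With no steroid effect, some EAT-10 or Bazaz test is significant in about 23% to 40% of trials. A secondary result favouring steroid without SWAL-QOL support occurs in about 10% to 21% of trials with SWAL-QOL judged at one visit, or about 7% to 18% at any visit.

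The ranges rest on assumed correlations of about 0.3 to 0.8, two-sided tests and normal approximations. Stronger correlation lowers them: at 0.9 throughout, the 12-test rate is still 13.5%. If change scores are also compared between arms, the number of tests rises.

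The documents do not support the stronger conclusion that the sponsor intends to rest the trial's claim on a secondary scale. They show only that nothing in the plan prevents it.

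**What to change.** 1. Name one post-operative visit for the primary SWAL-QOL comparison. This must come first.
2. In the Statistical Plan, replace the all-results sentence with a declaration of significance at two-sided 0.05 for that comparison only.
3. Word the null in the Hypothesis section in terms of SWAL-QOL, consistent with the Outcomes section.
4. Label all EAT-10, Bazaz, VAS and NDI comparisons supportive or exploratory, reported as between-arm estimates with 95% confidence intervals and no declaration of significance.
5. Optionally, test EAT-10 and Bazaz at the same visit in a fixed order, each only if the preceding test is significant, starting from SWAL-QOL. Either order is defensible, as the documents do not favour one, but it must be set before unblinding.

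The cost is a few sentences, with no extra patients or data. The downside is small: an isolated secondary result cannot be claimed as confirmatory when SWAL-QOL is negative. The Statistical Plan is written in the past tense. If outcome data by arm have already been seen, a newly added testing order would be post hoc and would not control error. In that case the secondary scales should simply be labelled exploratory.
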